### Summary:

The number (%) of subjects with the following will be summarized using the worst CTC grade ontreatment per subject.

- Post-baseline grade (summary of worst toxicity grade)
- Grade change from baseline
- Descriptive statistics of laboratory test result and their changes from baseline at scheduled nominal visit.

### Listing:

• A by-subject listing of these laboratory parameters will be provided. Laboratory abnormality criteria and laboratory results outside of normal range will be listed

## 7.6.7.1 Abnormal Hepatic Test

### Summary:

The number (%) of subjects with the following laboratory abnormalities from on-treatment evaluations will be summarized:

- Total bilirubin > 2 to  $\leq$  3 x ULN
- ALT or AST > 3 x ULN, > 5 x ULN, >10 x ULN, >12 x ULN, and > 20 x ULN
- ALT or AST > 20 x ULN *or* Total bilirubin > 3 x ULN
- Concurrent ALT or AST > 3 x ULN *and* Total bilirubin > 2 x ULN *or* INR > 1.5
- Concurrent ALT or AST > 5 to  $\leq 12 \text{ x}$  ULN *and* Total bilirubin  $\leq 2 \text{ x}$  ULN
- Concurrent ALT or AST > 12 to  $\leq 20$  x ULN *and* Total bilirubin  $\leq 2$  x ULN

A window of  $\pm$  3 days is applied to the concurrent abnormality. The days to onset is defined as the date abnormality criteria is first met - first dose date+1. For the concurrent abnormality, this date refers to the latter date when ALT or AST and Total bilirubin meets the abnormality criteria. The days to resolution refers to the resolution date - first abnormality onset date +1, where the resolution date is defined as the date of the visit when the given abnormality criteria is not met and there is no subsequent abnormality coming back. For concurrent abnormality, all lab test listed in the criteria needs to be nonmissing at the resolution visit. All lab assessment record collected in the study database will be used for the resolution evaluation regardless of whether it falls within the on-treatment window.

The definition of normal for the concurrent abnormality resolution definition is defined as:

- Total bilirubin > 2 to ≤ 3 x ULN Definition of normal: Total bilirubin ≤1.5 x ULN
- ALT or AST > 3 x ULN, > 5 x ULN, >10 x ULN, > 12 x ULN, and > 20 x ULN Definition of normal: ALT and AST < 2 x ULN
- ALT or AST > 20 x ULN or Total bilirubin > 3 x ULN Definition of normal: ALT and AST < 2 x ULN and Total bilirubin ≤1.5 x ULN
- Concurrent ALT or AST > 3 x ULN and Total bilirubin > 2 x ULN or INR > 1.5 Definition of normal: ALT and AST < 2 x ULN, Total bilirubin ≤1.5 x ULN and INR <= 1.5
- Concurrent ALT or AST > 5 to  $\leq 12 \text{ x}$  ULN and Total bilirubin  $\leq 2 \text{ x}$  ULN Definition of normal: ALT and AST < 2 x ULN and Total bilirubin  $\leq 1.5 \text{ x}$  ULN
- Concurrent ALT or AST > 12 to  $\leq 20$  x ULN and Total bilirubin  $\leq 2$  x ULN Definition of normal: ALT and AST < 2 x ULN and Total bilirubin  $\leq 1.5$  x UL

### Figure:

- Scatter plot of Total bilirubin peak vs AST peak
- Scatter plot of Total bilirubin peak vs ALT peak

On-treatment peak total bilirubin and on-treatment peak AST/ALT may or may not happen on the same day of liver testing.

## Listing:

A by-subject listing of these specific abnormalities will be provided if needed.

## 7.6.7.2 Abnormal Thyroid Test

## Summary:

The number (%) of subjects with abnormal thyroid test will be summarized as follows:

- Elevated TSH value > ULN and one of the below subcategorie is met:
  - with baseline TSH value  $\leq$  ULN
  - with at least one FT3/FT4 test value < LLN within 2-week window after the abnormal TSH test

  - with all FT3/FT4 test values  $\geq$  LLN within 2-week window after the abnormal TSH test
  - with F3/F4 missing within 2-week window after the abnormal TSH test
- Low TSH < LLN and one of the below subcategorie is met:
  - with baseline TSH value  $\geq$  LLN
  - with at least one FT3/FT4 test value > ULN within 2-week window after the abnormal TSH test
  - with all FT3/FT4 test values  $\leq$  ULN within 2-week window after the abnormal TSH test
  - with F3/F4 missing within 2-week window after the abnormal TSH test

The analyses will include lab values up to 100 days after last dose of study drug.

## Listing:

A by participant listing of these specific abnormalities will be provided

## 7.6.7.3 Abnormal Laboratory Test

## Summary:

The number of subjects with the following laboratory abnormalities from on-treatment evaluations will be summarized:

• CK > 10 x ULN, > 15 x ULN, > 20 x ULN

• LDH > 10 x ULN, > 15 x ULN, > 20 x ULN

### Listing:

A by subject listing of these specific abnormalities will be provided

## 7.6.8 Immunogenicity

### Summary:

The number (%) of subjects with the following anti-drug responses will be reported for immunogenicity subjects. The on-treatment period starts at first dose and beyond.

- baseline nivolumab ADA-positive
- baseline nivolumab ADA-negative
- baseline cabiralizumab ADA-positive
- baseline cabiralizumab ADA-negative
- nivolumab ADA-positive
- nivolumab ADA-negative
- cabiralizumab ADA-positive
- cabiralizumab ADA-negative

### Listing:

All collected immunogenicity will be listed with flags indicating baseline-positive sample, ADApositive sample or ADA-negative sample.

### **Clinical Implications:**

Effect of immunogenicity on clearance of cabiralizumab and nivolumab will be explored. The summary of trough concentration of cabiralizumab and nivolumab will be summarized respectively by postbaseline cabiralizumab and nivolumab ADA status.

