### 5.3.3 Pharmacokinetic Assessments

Blood samples for the PK evaluation of both cabiralizumab and nivolumab will be collected from all patients.

Patients enrolled in Phase 1a and Phase 1b will have blood drawn for measurement of serum cabiralizumab concentration. Blood samples will be collected during Cycle 1 and Cycle 8 on Days 1, 2, 4, and 8 as well as both before and after infusion for Cycle 2, 3 and 4. In addition, blood samples will be collected before the infusion on Cycles 5, 9, 13, and 21, then every 6 cycles while on treatment. A blood sample will also be collected for PK analysis during the End-of-Treatment Follow-up Period (28 [±7] days and 100 [±7] days post-last dose).

Patients enrolled in the 3-week dosing regimen cohort (1aD) will have additional blood sample drawn on Day 15 of Cycles 1 and 8. See Appendix C for specific collection time points.

Patients enrolled in Phase 1a and Phase 1b combination cohorts will have blood drawn for measurement of serum nivolumab concentration. Blood samples will be collected both before and at the end of infusion for Cycle 1 to Cycle 4. In addition, blood samples will be collected at the end of the infusion for Cycle 8 and before the infusion on Cycles 5, 9, 13, and 21. A blood sample will also be collected during the End-of-Treatment Follow-up Period.

Standard PK parameters will be determined based on serum cabiralizumab concentration-time data, as appropriate. Nivolumab accumulation will be evaluated as appropriate.

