### 5.3.4 Immunogenicity Assessments

Blood samples will be collected before the infusion on Cycles 1, 2, 3, 4, 5, 9, 13, and 21, and at the 28 (±7) days and 100 (±7) days End-of-Treatment Visits to measure ADA for cabiralizumab and nivolumab. ADA for cabiralizumab in serum will be measured by a validated bridging ECLA that utilizes Meso Scale Discovery (MSD) technology. ADA for nivolumab in serum will be measured by a validated ECLA method.

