#### 7.4.5 Immunogenicity

A listing will be provided of all available immunogenicity data for both cabiralizumab and nivolumab. Additionally, a listing of immunogenicity data from those patients with at least one positive ADA at any time point will be provided by dose level. The frequency of patients with at least one positive ADA assessment, and frequency of patients who develop ADA after a negative baseline assessment will be provided by dose. To examine the potential relationship between immunogenicity and safety, the frequency and type of AEs of special interest may be examined by overall immunogenicity status. Associations between pre-dose concentrations of cabiralizumab or nivolumab and corresponding ADA assessments may be explored.

[REDACTED]

[REDACTED]

[REDACTED]

[Redacted text block]

[Redacted text block]

[Redacted text block]

- | [Redacted list item]
- | [Redacted list item]
- | [Redacted list item]
- | [Redacted list item]
- | [Redacted list item]
- | [Redacted list item]
- | [Redacted list item]
- | [Redacted list item]
- | [Redacted list item]
- | [Redacted list item]
- | [Redacted list item]
- | [Redacted list item]

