#### **Table 1. Sample ADA Status**

Sample ADA Status	Definition	
Baseline ADA-positive sample	ADA is detected in the last sample before initiation of treatment	
Baseline ADA-negative sample	ADA is not detected in the last sample before initiation of treatment	
ADA-positive sample	1) an ADA detected (positive seroconversion) sample in a subject for whom ADA is not detected at baseline, or (2) an ADA detected sample with ADA titer to be at least 4-fold or greater ( $\geq$ ) than baseline positive titer	
ADA-negative sample	ADA sample that is not deemed ADA-positive	

Next, using the sample ADA status, subject ADA status is defined as follows:

ADA Status	Definition	
Baseline ADA-positive A subject with baseline ADA-positive sample		
ADA-positive	A subject with at least one ADA positive-sample relative to baseline at any time after initiation of treatment	
ADA-negative	A subject with no ADA-positive sample after the initiation of treatment	

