### If Year of AE start date is missing:

If the year of AE start is missing or AE start date is completely missing then query site with no imputation. Also compare the full (or partial) AE end date to the first dose date. If the AE end date is before the first dose date then the AE should be considered as a pretreatment AE. Otherwise, the AE will be considered as TEAE.

·	Summary of Changes						
Version	Summary of Changes						
1.0	Original version						
2.0	
 
Added that PK analyses will be presented by individual or combined cohort by different dose and regimen
 
						
	• Removed PFS, ORR, and DOR analysis for colon rectum cancer						
	• Corrected '1aD' to '1aD1' in calculation of exposure and relative dose intensity						
	Removed Screened Population from the analysis						
• Changed window of concomitant medication from 10 to 100 days after last dose of any study drug (or until subsequent anticancer therapy in long-term follow-up							
	• Italicized 'and' / 'or' in the concurrent hepatica abnormality criteria for clarification						
	Changed immunogenicity on-treatment period						
	• Added baseline nivolumab ADA-negative and baseline cabiralizumab ADA-negative in immunogenicity summary						
	• Changed subgroup summary of trough concentration of cabiralizumab and nivolumab from by baseline ADA status to by postbaseline ADA status						
	• Reference of 'CLT' was changed to 'CL" in SAP text						
	• Reference of 'T HALF' was changed to 't1/2' in SAP text						
	• Added definition for MRT, t1/2, and Vss.						
• Updated version of Phoenix WinNonLin							
	Clarified MedDRA version						

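### SAP 7.6.8 does not say at which level ADA status groups the troughs; under the subject-level definition, troughs drawn before the first positive sample count as ADA-positive

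*SAP*

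**What the plan says.** Under Clinical Implications, SAP 7.6.8 says that the effect of immunogenicity on clearance will be explored, and that troughs of cabiralizumab and nivolumab "will be summarized respectively by postbaseline cabiralizumab and nivolumab ADA status". It does not say whether status is per subject or per sample, or whether troughs are shown by visit or pooled.

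SAP 4.2 defines both levels. Table 1 classes each sample; one route to positive is "an ADA detected (positive seroconversion) sample in a subject for whom ADA is not detected at baseline", the other a titer at least four times a positive baseline titer. The companion subject table, whose column is headed simply ADA Status, defines positive as "A subject with at least one ADA positive-sample relative to baseline at any time after initiation of treatment". SAP 7.6.8 sets the immunogenicity window with "The on-treatment period starts at first dose and beyond", which has no end.

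On sampling, protocol 5.3.4 states for ADA to both drugs: "Blood samples will be collected before the infusion on Cycles 1, 2, 3, 4, 5, 9, 13, and 21", plus the 28-day and 100-day End-of-Treatment Visits. Protocol 5.3.3 has cabiralizumab PK drawn "both before and after infusion for Cycle 2, 3 and 4", and before infusion at Cycles 5, 9, 13 and 21; nivolumab has pre-infusion samples at the same cycles.

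Protocol 7.4.5 allows a matched look: "Associations between pre-dose concentrations of cabiralizumab or nivolumab and corresponding ADA assessments may be explored". The SAP lists every sample with its ADA flag but specifies no summary that uses the flags against concentration.

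**The concern.** A trough belongs to one dosing interval, whereas subject-level ADA status is fixed for the whole study. Grouping by the fixed status lets a later result classify an earlier concentration. A patient first positive at Cycle 9 contributes Cycle 2, 3, 4 and 5 troughs, all drawn while antibody-negative, to the ADA-positive row. A patient first positive only at the 28- or 100-day visit contributes every on-treatment trough to that row.

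There is a second, smaller effect. To be found positive, a patient must stay under observation long enough to be sampled and convert. The ever-positive group therefore leans toward patients with longer treatment, whose troughs may differ for other reasons.

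At stake is how the SAP's one tabulated comparison of antibody status with exposure is read. PK and immunogenicity are secondary objectives in both phases. If the two rows look alike, a reader may conclude that antibodies do not matter for exposure when the grouping has blurred the contrast.

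**Working it through.** The plan gives no figure to reproduce: it states no ADA incidence, onset time or effect on trough. The schedule can be checked exactly; the dilution can only be illustrated.

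**Step 1: paired draws.** Setting protocol 5.3.3 beside 5.3.4, pre-dose PK and ADA coincide after first dose at Cycles 2, 3, 4, 5, 9, 13 and 21, so n = 7 for each drug. Cycle 8 is left out because the protocol lists it inconsistently across sections; draws after Cycle 21 are also left out.

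**Step 2: troughs before the first positive sample.** Let k be the number of the n = 7 paired troughs that precede it. Assume that ADA multiplies trough by a constant g from the first positive sample onward, and not before. On the geometric scale, pooling all seven visits of an ever-positive patient gives

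observed ratio = g^((n − k)/n).

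| First positive at | k of 7 | g = 0.3 | g = 0.5 | g = 0.7 |
|---|---|---|---|---|
| Cycle 2 | 0 | 0.30 | 0.50 | 0.70 |
| Cycle 3 | 1 | 0.36 | 0.55 | 0.74 |
| Cycle 5 | 3 | 0.50 | 0.67 | 0.82 |
| Cycle 9 | 4 | 0.60 | 0.74 | 0.86 |
| Cycle 13 | 5 | 0.71 | 0.82 | 0.90 |
| Cycle 21 | 6 | 0.84 | 0.91 | 0.95 |
| Follow-up only | 7 | 1.00 | 1.00 | 1.00 |

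Example: first positive at Cycle 5 with g = 0.5 gives 0.5^(4/7) = 0.67.

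**Step 3: a population with dropout.** The table takes patients who reach Cycle 21, which many will not. A simulation used these assumptions, none from the documents: 30% of patients would convert; log-normal troughs with CV 60%; log-normal time on treatment with median 5 cycles (log-SD 0.6 to 1.0); g = 0.50; on-treatment samples only. Geometric mean ratios, ADA-positive to ADA-negative, under subject-level grouping:

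- Conversion spread evenly over Cycles 2, 3, 4, 5, 9 and 13: pooled 0.65. By visit: 0.81-0.83 (C2), 0.69-0.72 (C3), 0.60-0.64 (C4), 0.54-0.57 (C5), about 0.53 (C9), about 0.50 (C13).
- Same, with higher-trough patients staying longer (correlation 0.5): pooled 0.70-0.71, and above 0.90 at C2.
- Conversion only at Cycles 2 or 3, no correlation: pooled about 0.55, and 0.50 at every visit from C3.

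The by-visit pattern follows from ratio = g^s, where s is the share of eventually positive patients already positive at that visit. A reading of 0.82 at Cycle 2 corresponds to s = ln(0.82)/ln(0.50) = 0.29, so about seven in ten of the patients labelled positive at that visit had not yet converted.

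**Step 4: same-draw classification.** Under the same model, grouping each trough by the ADA result of its own draw returns 0.49 to 0.51 at every visit. Pooled over visits it gives 0.50 without the correlation and 0.53-0.54 with it, so the table should be read by visit.

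**The case against.** The strongest reply is that the SAP never says the grouping is by subject. That is correct. Postbaseline ADA status is not a defined term, both levels are defined, and for Phase 1b SAP 4.2 sends the reader to Table 1, whose title refers to samples. A reader might infer that the SAP prescribes the any-time definition for this table; the text does not go that far. The subject-level reading is only the more natural one. The SAP change log points the same way by calling this a subgroup summary ("Changed subgroup summary of trough concentration of cabiralizumab and nivolumab from by baseline ADA status to by postbaseline ADA status"), but it is context, not a rule. If sample level was intended, the SAP still needs to say so, because two programmers could build different tables.

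A reader might also infer that this is the only planned look at antibodies and exposure. It is not. The same section plans to explore clearance, protocol 7.4.5 allows the matched analysis, and sample flags will be listed. What is missing is a specified summary that respects timing.

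A third tempting inference is that the grouping always biases toward no effect. That depends on the assumptions. If patients with lower underlying exposure are more prone to form ADA (assumed latent correlation 0.4, true ratio 0.50), subject-level grouping reads 0.47 and sample-level 0.37. With no true effect they read 0.72 and about 0.75. So one bias can offset another, and same-draw grouping is not a cure for confounding. This does not justify labelling a trough drawn before conversion as ADA-positive.

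One further limit stands under either grouping. SAP 7.7.1 treats values below the quantitation limit as missing when means are formed, so strongly suppressed troughs could drop out of the comparison.

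**Conclusion.** The point holds as an unspecified grouping level with a foreseeable consequence. On the natural reading, anywhere from 0 of 7 paired troughs (first positive at Cycle 2) to 7 of 7 (first positive only in follow-up) are counted as ADA-positive before any positive sample exists. That much follows from the definitions and the schedule alone.

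The dilution figures rest on assumed incidence, onset and effect, and on ADA acting only from the first positive sample. They show that the problem ranges from slight with early onset to material for a pooled table with spread onset, and that a by-visit table is little affected at late visits. They are not estimates for this trial.

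Severity is minor. The display is descriptive, no decision rule in the documents uses it, and the ADA incidence summary itself is unaffected.

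**What to change.** In SAP 7.6.8, under Clinical Implications:

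- State the level of ADA status used for the trough summary.
- Make the main display trough by visit, grouped by the Table 1 sample status of the same pre-dose draw, at Cycles 2, 3, 4, 5, 9, 13 and 21. This carries out the matching that protocol 7.4.5 foresees.
- Show troughs without a same-visit ADA sample in a separate row, or flag any carried-forward status. After Cycle 5 the ADA draws listed in protocol 5.3.4 are four to eight cycles apart, so a carried-forward status can itself be wrong.
- Keep the subject-level table, if wanted, as a secondary display labelled as such.
- Add a note that the matched table removes the timing misclassification but not confounding by underlying exposure.

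The cost is a change of SAP wording and one extra table. No new samples are needed. Some cells will be small, particularly for later visits and individual cohorts.

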### 7.6.9 Vital Sign

For vital sign parameters of heart rate, blood pressure (systolic and diastolic), temperature, respiration rate, pulse oximetry, and weight, descriptive statistics of measured value and their changes from baseline will be summarized for each scheduled assessment. Additionally, the actual value and change from baseline for the maximum value, minimum value, and last available assessment will be summarized with descriptive statistics. The on-treatment period starts at first dose and ends at 100 days after last study therapy.

Vital signs data will be listed by subject at each visit.

#### 7.6.10 Electrocardiograms

For12-lead ECG parameters (HR and PR, RR, QRS, QT, QTc (QTcF, QTcB and other) intervals), the actual value and change from baseline for the maximum value, minimum value, and last available assessment will be summarized. The on-treatment period starts at first dose and ends at 100 days after last study therapy.

Shift tables will be presented for overall ECG result showing the number and frequency of subjects with normal, abnormal clinical significant, and abnormal not clinically significant at the baseline to post-dose scheduled visits.

All recorded electrocardiograms will be listed for all treated subjects.

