  - Chemistry** includes CK (creatinine kinase), AST (aspartate transaminase), ALT (alanine transaminase), alkaline phosphatase, bicarbonate, bilirubin, (direct and total), BUN (blood urea nitrogen), calcium, chloride, creatinine, glucose, LDH (lactate dehydrogenase), phosphorus, potassium, sodium, and, if applicable, serum pregnancy. Albumin, amylase, lipase, thyroid panel includes TSH, Free T3 and Free T4, PT/INR, and PTT (aPTT) perform at Screening and as indicated. If CK elevation is clinically significant, obtain troponins (cardiac and skeletal), CK isoenzymes, aldolase, and ECG; repeat CK and these additional tests within 48 hours or other interval as clinically indicated, until resolved or stable. If either AST or ALT is elevated, obtain total serum bilirubin, alkaline phosphatase; repeat within 48 hours or other interval, as clinically indicated, until resolved or stable. Additional tests may be obtained at any time, if clinically indicated. If a patient is being followed for a tumor marker (e.g. CA-125, or others), a sample for the tumor marker should be obtained at screening and every other cycle, or if clinically indicated during the study
  - Urinalysis:** Urine dipstick will only be done at screening, and when clinically indicated.
- j. Obtain ECG records at Screening and the Day 28 post last infusion End-of-Treatment Visit (after PK blood draw, record exact time). Additional ECGs should be obtained at any time, if serum CK or cardiac troponin is elevated; if abnormal (excluding sinus tachycardia), ECGs should be obtained (if clinically indicated), until the abnormality is resolved or clinically stable. Additional ECGs may be obtained at any time, if clinically indicated. ECGs for each patient should be obtained from the same machine whenever possible. To minimize variability, it is important that patients be in a resting position for at least 5 minutes prior to each ECG evaluation. Body position should be consistently maintained for each ECG evaluation to prevent changes in heart rate. Environmental distractions (e.g., television, radio, conversation) should be avoided during the pre-ECG resting period and during ECG recording.

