**Chemistry** includes CK (creatinine kinase), AST (aspartate transaminase), ALT (alanine transaminase), alkaline phosphatase bicarbonate, bilirubin, (direct and total), BUN (blood urea nitrogen), calcium, chloride, creatinine, glucose, LDH (lactate dehydrogenase), phosphorus, potassium, sodium, and, if applicable, serum pregnancy. Albumin, amylase, lipase, thyroid panel includes TSH, Free T3 and Free T4, PT/INR, and PTT (aPTT) perform at Screening and as indicated, If CK elevation is clinically significant, obtain troponins (cardiac and skeletal), CK isoenzymes, aldolase, and ECG; repeat CK and these additional tests within 48 hours or other interval as clinically indicated, until resolved or stable. If either AST or ALT is elevated, obtain total serum bilirubin, alkaline phosphatase; repeat within 48 hours or other interval, as clinically indicated, until resolved or stable. Additional tests may be obtained at any time, if clinically indicated. If a patient is being followed for a tumor marker (e.g. CA-125, or others), a sample for the tumor marker should be obtained at screening and every other cycle, or if clinically indicated during the study.  
**Urinalysis:** Urine dipstick will only be done at screening, and when clinically indicated.
- i. Obtain ECG records at screening and the Day 28 post last infusion End-of-Treatment Visit (after PK/PD blood draw, record exact time). Additional ECGs should be obtained at any time, if serum CK or cardiac troponin is elevated; if abnormal (excluding sinus tachycardia), ECGs should be obtained (if clinically indicated), until the abnormality is resolved or clinically stable. ECGs for each patient should be obtained from the same machine whenever possible. To minimize variability, it is important that patients be in a resting position for at least 5 minutes prior to each ECG evaluation. Body position should be consistently maintained for each ECG evaluation to prevent changes in heart rate. Environmental distractions (e.g., television, radio, conversation) should be avoided during the pre-ECG resting period and during ECG recording. Additional tests may be obtained at any time, if clinically indicated.

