### 4 ENDPOINTS

### 4.1 **Primary Endpoints**

#### Phase 1a

- Safety
  - The incidence of Grade 3 and Grade 4 AEs and clinical laboratory abnormalities defined as DLTs
  - o The incidence of AEs, clinical laboratory abnormalities, and ECG abnormalities

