#### Phase 1b

• Efficacy

ORR is defined as the total number of subjects with confirmed responses of either complete response (CR) or partial response (PR) divided by the total number of subjects in the response-evaluable population (as defined in section 7.2) per Response Evaluation Criteria in Solid Tumors, version 1.1 (RECIST v1.1) by investigator assessment

• Safety

- The incidence of adverse events (AEs), serious adverse events (SAEs), clinical laboratory abnormalities, and ECG abnormalities
- The incidence of treatment discontinuations, modifications, and interruptions due to adverse events
- Grade 3 and Grade 4 AEs and clinical laboratory abnormalities

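### The only table that counts abnormal ECGs is tied to scheduled visits, but every ECG between first and last dose is for cause, so this part of the primary safety endpoint is incompletely estimated

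*SAP*

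**What the plan says.** SAP 4.1 names ECG abnormalities in the primary safety endpoint of both phases. For Phase 1a it lists "The incidence of AEs, clinical laboratory abnormalities, and ECG abnormalities"; for Phase 1b, "The incidence of adverse events (AEs), serious adverse events (SAEs), clinical laboratory abnormalities, and ECG abnormalities".

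SAP 7.6.10 then plans three ECG outputs:

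- Numeric summaries of heart rate and the PR, RR, QRS, QT and QTc intervals: "the actual value and change from baseline for the maximum value, minimum value, and last available assessment will be summarized". The section sets an on-treatment period from first dose to 100 days after the last study therapy.
- A shift table of the overall ECG reading, classed as normal, "abnormal clinical significant, and abnormal not clinically significant at the baseline to post-dose scheduled visits".
- A listing: "All recorded electrocardiograms will be listed for all treated subjects".

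The protocol fixes when ECGs are taken. Appendix A, note j (Phase 1a) says "Obtain ECG records at Screening and the Day 28 post last infusion End-of-Treatment Visit", and Appendix B, note i (Phase 1b) says "Obtain ECG records at screening and the Day 28 post last infusion End-of-Treatment Visit". Further ECGs are event-driven: "Additional ECGs should be obtained at any time, if serum CK or cardiac troponin is elevated", and otherwise when clinically indicated.

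**The concern.** The endpoint asks how many patients had an ECG abnormality. The table that comes closest to answering is organised by scheduled visit, while the schedule places no routine ECG between first and last dose. The ECGs most likely to show a treatment effect are those prompted by raised CK or troponin, or by symptoms, and these are the ones whose place in the table is either excluded or undefined.

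This matters more here than in many oncology trials. CK elevation is clearly anticipated: the DLT definition (protocol 3.1.2.1.1) makes specific allowance for it, and SAP 7.6.7.3 tabulates CK above 10, 15 and 20 times ULN. SAP 7.6.6 names myocarditis among the events of special interest. If the shift table is programmed as written, a reader of the study report could take a low abnormal count as evidence about the treatment period when it reflects mainly the 28-day follow-up visit.

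**Working it through.** No published figure has to be reproduced; the check traces the endpoint to the tables and the tables to the schedule.

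**1. Outputs that count patients with an abnormal ECG.** Of the three outputs in SAP 7.6.10, the numeric summaries describe interval values and the listing shows individual records. Only the shift table counts patients by normal or abnormal reading. No QTc threshold category is planned.

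- Tables counting patients with an abnormal ECG: 1
- Tables counting any, or worst, on-treatment abnormality including unscheduled ECGs: 0

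**2. Scheduled ECGs per patient.** The inputs are Appendices A and B with their notes, the screening sections (protocol 5.2.1.1, 5.2.2.1, 5.2.3.1) and the End-of-Treatment sections (5.2.1.9, 5.2.2.11, 5.2.3.8). The End-of-Treatment sections limit the ECG to the 28-day visit, so the 100-day visit has none.

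- Baseline: 1 (screening)
- Between first and last dose: 0
- After the last dose: 1, between 28 − 7 = 21 and 28 + 7 = 35 days

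**3. How each kind of post-dose ECG meets the shift table.**

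| ECG | In the shift table? |
|---|---|
| 28-day End-of-Treatment ECG | Yes |
| For cause, at a scheduled dosing visit (allowed by protocol 5.3.1) | Not stated |
| For cause, outside any scheduled visit | No |

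The third row is a realistic case. For a clinically significant CK rise, Appendix A note i and Appendix B note h call for an ECG along with troponins and other tests, repeated within 48 hours or at another clinically indicated interval. Cycles last 14 days (21 in Cohort 1aD). Apart from Cycles 1 and 8, the schedules show no visit between Day 1 of one cycle and Day 1 of the next, so such repeats can readily fall between visits.

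**4. Patient level versus visit level.** Even if the second row were admitted, a by-visit shift gives a count at each visit. It does not give the number of patients with at least one abnormal ECG. A patient who misses the 28-day visit and has no ECG at another scheduled visit contributes nothing.

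**5. The SAP's own convention elsewhere.** Laboratory results are summarised by worst on-treatment grade (SAP 7.6.7). The ECOG shift runs from baseline to the maximum grade on treatment (SAP 7.6.12). The ECG shift departs from this, although 7.6.10 defines the same 100-day on-treatment period.

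**The case against.** The best reply is that these ECGs can reach the report by other routes, and much of it stands.

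- **Adverse events.** Protocol section 6 defines an adverse event broadly enough to include an unfavourable sign. An abnormal ECG reported in that way enters the treatment-emergent tables of SAP 7.6, and the serious, discontinuation or special-interest tables if it qualifies. This narrows the gap without closing it. Protocol 6.4 sets capture rules for laboratory abnormalities, but the available text has no equivalent for ECGs, and a reading judged not clinically significant may never be reported as an event. The endpoint also lists ECG abnormalities separately from adverse events.
- **Interval summaries and listing.** Maximum and minimum values are not restricted to scheduled visits, and every tracing is listed. This stands, but neither output is an incidence, and an abnormality expressed only in the overall reading does not appear among the intervals.
- **Visits, not ECGs.** The SAP restricts the table to scheduled visits, not to scheduled ECGs. A clinically indicated ECG at a dosing visit could therefore be included. This too stands; it makes the plan ambiguous rather than complete.
- **Limits of any remedy.** With no routine on-treatment ECG, a worst-case table mixes for-cause tracings in some patients with a single follow-up tracing in others. A SAP sentence cannot repair the schedule. It can make the count complete for the data collected and state its limits.
- **Consequence.** All analyses are descriptive (protocol section 7), and dose escalation rests on DLTs and committee review, not on this table.

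A reader might go further and infer that every abnormality seen only on a for-cause ECG disappears, or that the endpoint rests on one tracing per patient. The first three points above show that the documents do not support either reading. Nor should the 28-day ECG be described as taken off drug: the SAP's on-treatment period runs to 100 days after the last therapy, so days 21 to 35 lie inside it.

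**Conclusion.** The point holds in a limited form. The only count of patients with an abnormal ECG excludes for-cause ECGs taken outside scheduled visits and leaves the status of those taken at dosing visits undefined. No table gives a patient-level count of any on-treatment ECG abnormality. This component of the primary safety endpoint is therefore incompletely estimated in both phases; it is not wholly lost.

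The size can be stated only structurally: one scheduled post-dose ECG, none between first and last dose, and no worst-on-treatment table. The documents give neither the frequency of for-cause ECGs nor the proportion abnormal, so no number of missed patients can be derived.

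The conclusion assumes that the table is programmed as 7.6.10 is worded, and that the redacted material contains no further ECG schedule or ECG-abnormality table. It is an inexpensive improvement to a descriptive safety analysis and does not affect dose decisions.

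**What to change.** In SAP 7.6.10:

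- Define the shift as baseline to the worst post-baseline overall ECG result in the on-treatment period already stated there (first dose to 100 days after last therapy), including unscheduled ECGs.
- Report the number of patients with at least one post-baseline ECG and use it as the denominator.
- Keep the shift to the 28-day visit as a separate column, since it is the one assessment planned for everyone.
- Add a footnote that ECGs between first and last dose are taken selectively for cause, so the count is not an incidence under uniform surveillance.

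The cost is one amended sentence, one worst-case derivation and a footnote. No new data are needed, because all recorded ECGs are already to be listed. The drawback is the selective sampling, which the footnote and the separate 28-day column make visible.
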